9.2 Sample Size Determination

Statistical calculations:

Sample size (for unknown population size) was determined based upon a 95% confidence level (Z-score 1.96), standard deviation of 0.5, and a margin of error (confidence interval) of 10%. [[qualtrics.com/experience-management/research/determine-sample-size](https://www.qualtrics.com/experience-management/research/determine-sample-size)]

- Necessary Sample Size = $((Z\text{-score})^2 * \text{StdDev}^2 * (1-\text{StdDev}^2)) / (\text{margin of error})^2$
 - $((1.96)^2 * 0.5^2 * (1-0.5^2)) / (0.1)^2 =$
 - $(3.8416 * 0.25) / (0.01) =$
 - 96.04
 - **At least 97 performed airway procedures are needed to have adequate power to test our hypotheses for this study**

We will screen at least 175 patients, and assuming a 10-15% drop-out/screen failure rate, plan to enroll at least 150 patient subjects on a rolling basis during weeks 2 - 6 of the trial to evaluate the use of a novel biocontainment and aerosol evacuation system. The study should be adequately powered to assess secondary endpoints. Some of the sub-analyses may be underpowered depending on the characteristics of the recruited patients.

At defined intervals (see Section 1.3 Schema), we will perform interim analysis to determine changes to sample size based on subject drop out/withdrawal.

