9 STATISTICAL CONSIDERATIONS

9.1 *Statistical Hypotheses*

We hypothesize that the biocontainment device will be a safe and effective option for performing airway procedures in patients while also providing additional protection during an aerosol generating procedure.

Primary Efficacy Endpoints:

1. We hypothesize that the time to perform an airway procedure with the biocontainment device will be equivalent to time for airway procedure without the biocontainment device. Alternatively, there will be prolonged airway procedures times with the device. This endpoint will be analyzed every two weeks.
2. We anticipate that the number of AEs or ADEs will be low and will also decrease over time. This endpoint will be analyzed on a weekly basis.

Secondary Efficacy Endpoints:

1. We hypothesize that the median Likert ratings for User subject device comfort will be weighted toward “strongly agree”. Alternatively, we will see ratings favoring “neutral” or “disagree” for user subject device comfort.
2. We hypothesize that the median Likert ratings for User subject additional healthcare burden comfort will be weighted toward “strongly disagree”. Alternatively, we will see ratings favoring “neutral” or “agree” on increased healthcare burden.
3. The median Likert ratings for the Patient Experience survey will be weighted toward minimal patient discomfort or anxiety. Alternatively, we will see ratings favoring increased patient discomfort or anxiety inside the device.
3. We anticipate that the median Likert ratings of the patient experience post-survey will indicate overall good user comfort and low levels of anxiety or claustrophobia in the device.

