9.4.2 Analysis of the Primary Efficacy Endpoint(s)

Primary Endpoints:

1. Assessment of time to complete an airway procedure with or without the biocontainment device. The time is measured as a single quantitative measure at the end of the procedure. The initial starting time (T0) is defined as “time the mask is removed from the patient just prior to initiation of the airway procedure”. End time (T1) is defined as the time that the airway procedure is completed with a secure airway defined as the

time the airway device is secured to the airway circuit. Data will be presented as median amount of time for a given procedure with or without the biocontainment device and statistical significance will be determined by analysis of variance (ANOVA). Additionally, a multiple regression model will be created using covariates of subject user experience, number of prior uses with the device, and patient specific factors (co-morbid conditions, BMI, Mallampati score). This will help determine the critical factors associated with time to use the device.

2. The total number of AEs and ADEs will be presented. This will be broken down by specific AE or ADE. Logistic regression will be used to assess possible contributing factors to AEs or ADEs including subject user experience, airway procedure performed, patient-specific factors (BMI, co-morbid conditions, Mallampati score). We anticipate a low number of AEs/ADEs and as such, statistically rigorous regression analyses may be limited by a low overall number of events.

Statistical analyses will be performed on all data points, however, a sub-analysis will be performed on participants without any missing data points.

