9.4.5 Planned Interim Analyses

An interim analysis will be performed after 50% enrollment (approximately 4 weeks) on primary and secondary outcomes. If the total number of AEs or ADEs is trending upward over time, the study would be paused until further assessment of AE/ADEs by the study Sponsor or their qualified designee would be performed as described in [Section 8](#).

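### Section 9.2 claims power on the basis of a one-group precision formula; both power statements are unsupported as written, although underpowering is not shown

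*Combined protocol and SAP*

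**What the plan says.** Section 9.2 lists its inputs as a 95% confidence level (z = 1.96), "standard deviation of 0.5, and a margin of error (confidence interval) of 10" percent. The substituted line of the formula contains "1.96)^2 * 0.5^2 * (1-0.5^2"; the next line multiplies 3.8416 by 0.25, divides by 0.01 and arrives at 96.04. The conclusion is "At least 97 performed airway procedures are needed to have adequate power to test our hypotheses for this study". The section then plans to enrol at least 150 patients and adds "The study should be adequately powered to assess secondary endpoints". The only reservation is that some sub-analyses may lack power.

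The hypotheses lie elsewhere. Section 9.1 expects that "the time to perform an airway procedure with the biocontainment device will be equivalent to time for airway procedure without the biocontainment device". Section 6.3 randomises 2:1, and Section 1.3 sets the target at 100 procedures with the device and 50 without. For procedure time, Section 9.4.2 says that "statistical significance will be determined by analysis of variance (ANOVA", with medians presented. The second primary endpoint is the number of AEs and ADEs, expected to be low and to fall over time (Section 9.1). The secondary endpoints are median Likert ratings, tested by Chi-square (Section 9.4.3).

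**The concern.** A power statement needs a test, an effect or margin, a measure of variability, an error rate and the group sizes. Section 9.2 supplies a confidence level and a margin of error for a single group. No other section gives a target power, an SD of procedure time, a detectable difference or an equivalence margin.

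The main stake is interpretation. The plan combines a hypothesis of equivalence, a test for a difference, and an assurance of sufficient power. A reader given those three together could take a non-significant ANOVA as evidence that the device does not lengthen airway procedures, when the protocol has never worked out how large a difference the trial could miss. The assurance on secondary endpoints has no calculation of its own.

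**Working it through.** **1. The plan's own figure.** Inputs from Section 9.2: z = 1.96, SD 0.5, margin 0.10.

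- Formula as printed, z² × SD² × (1 − SD²) / margin²: 3.8416 × 0.25 × 0.75 / 0.01 = 72.03.
- Formula evidently intended, z² × p(1 − p) / margin² with p = 0.5: 3.8416 × 0.25 / 0.01 = 96.04, rounded up to 97.
- Read as a one-sample mean, (1.96 × 0.5 / 0.10)² = 96.04 as well.

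So 97 reproduces, and on either reading it is a one-group precision figure. The slip is in the symbolic line and its first substitution only.

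**2. Why this is not power.** Suppose the 10-point margin were treated as a difference to detect in a one-sample test with n = 97. The standard error is √(0.25/97) = 0.0508, and power is Φ(0.10/0.0508 − 1.96), about 50%.

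**3. What the planned comparison of procedure time can resolve.** Assumptions: normal approximation, independent procedures, procedure types pooled, all 150 analysed, a single analysis at 5%. The documents give no SD, so results are in SD units.

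- SE = √(1/100 + 1/50) = 0.1732 SD.
- 95% CI half-width: 1.960 × 0.1732 = 0.34 SD.
- 80% power, two-sided 5%: (1.960 + 0.842) × 0.1732 = 0.49 SD.
- 80% power, one-sided 5%: (1.645 + 0.842) × 0.1732 = 0.43 SD.
- Two-sided power, Φ(d/SE − 1.96): about 21% at d = 0.2 SD, 41% at 0.3 SD, 64% at 0.4 SD, 82% at 0.5 SD and 93% at 0.6 SD.

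Across that range power goes from poor to good. Without an SD and a difference that matters, adequacy can be neither confirmed nor refuted.

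**4. AE/ADE co-primary endpoint.** A one-group precision fits best here: the proportion of about 100 device procedures with an event, taken as independent.

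- At an assumed 5% rate: 1.96 × √(0.05 × 0.95 / 100) = 0.043, or ±4.3 points.
- With no events in 100: one-sided 95% upper bound 1 − 0.05^(1/100) = 0.0295, about 3.0%.

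These figures bear on whether the rate is low. They say nothing about a decline over time.

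**5. Secondary endpoints.**

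- The patient survey goes only to patients randomised to the device (Section 8.1), planned as 100. For a proportion near 0.5, 1.96 × √(0.25/100) gives ±9.8 points. The endpoint is a median Likert rating, so this applies only if a response is dichotomised and all 100 reply. It is not power for a Chi-square test.
- The user surveys are repeated ratings by 15 to 20 users (Section 5.5), collected daily according to Sections 1.3 and 8.1 or after each use according to Section 8.2. A precision for about 100 independent cases does not describe them.

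**The case against.** The study is labelled a safety and feasibility study (Sections 2.2 and 4.2), and a precision rationale is acceptable for that purpose. It enrols 150, not 97, and the device arm of 100 exceeds 97. The section concedes that sub-analyses may be underpowered. No section says that a non-significant result will be read as equivalence. The formula slip does not change the number.

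All of this is fair, and it limits the point. It does not rescue the two claims. The text asserts power to test hypotheses, not precision; no power is derived at 150 either; and the reservation covers sub-analyses only.

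Three stronger readings are tempting and are not supported:

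- That the trial is underpowered. The documents give no SD or margin against which to judge this.
- That the correct sample size is 72 or 73. The substituted arithmetic shows that p(1 − p) was meant.
- That the sponsor plans to infer equivalence from a non-significant ANOVA. The wording invites this but does not state it.

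**Conclusion.** The concern holds as a defect of justification. Section 9.2 contains a one-group precision calculation, and both power statements are unsupported as written. The figure of 97 is valid only as the number needed to estimate one proportion near 0.5 to within about 10 points.

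Under the assumptions listed in the working, the planned 100 versus 50 gives a half-width of about 0.34 SD and 80% power for about 0.49 SD (two-sided) or 0.43 SD (one-sided). Those figures would change with per-protocol exclusions (Section 9.3), clustering by user, analysis by procedure type, or a median or non-parametric analysis (Sections 9.4.1 and 9.4.2). Repeated looks would also change them: Section 9.1 says "This endpoint will be analyzed every two weeks" and Section 9.4.5 says "An interim analysis will be performed after 50% enrollment (approximately 4 weeks) on primary and secondary outcomes". This should be corrected, but it is no ground for changing the size of the trial.

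**What to change.** Leave the planned 100:50 unchanged and reword Section 9.2:

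1. Correct the formula to z² × p(1 − p) / margin², and describe 97 only as the number needed to estimate a single proportion near 0.5 to within about 10 points.
2. Delete both power claims.
3. For procedure time, state: *Assuming a normal approximation, independent procedures, procedure types pooled, all 150 analysed and a single analysis at 5%, 100 versus 50 gives a 95% CI half-width of about 0.34 SD and 80% power for a difference of about 0.49 SD (two-sided) or 0.43 SD (one-sided). A non-significant ANOVA does not show equivalence.* List the features named in the verdict that would alter these figures. If the sponsor wants to claim equivalence, it must instead state a margin, SD, alpha, power and the 2:1 ratio.
4. For AEs/ADEs, give the precision for about 100 device procedures, such as ±4.3 points at an assumed 5% rate, or an upper bound of about 3.0% if no events occur.
5. For the secondary endpoints, claim no power. Say that ±9.8 points applies to the patient survey only if a response is dichotomised and all 100 reply, and that it does not apply to the user surveys.

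The cost is rewording, with no extra patients. The downside is a less favourable justification, expressed in SD units until an SD of procedure time is available.

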9.3 Populations for Analyses

For this study, a per-protocol analysis dataset will be obtained. Participants (user and patient subjects) who complied with the protocol will be used to create a dataset. This population for analyses will in effect allow us to analyze outcomes related to the advantages and disadvantages of the protective device of interest. For example, the number of proceduralists who utilized the protective device, overall device utilization and perceived comfort level, added healthcare burden and training level with the device.

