6.3 Measures to Minimize Bias: Randomization and Blinding

Randomization will be done to assign patients to intubation with or without the biocontainment device in a 2:1 fashion. This will allow for analysis of patient-related intubation factors as well as user-related intubation factors as part of the feasibility analysis. Blinding is not possible with this study as all users and patients will be aware of the presence of the device intervention. To help minimize bias in the data analysis, results of all data analysis will be assessed by a neutral, third-party with expertise in statistical analysis.

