6.4 Study Intervention Compliance

Use of the device will be assessed based on review of videos of the procedures, completion of quality use surveys by user subjects, and completion of the surveys by patient subjects. Each device will have a unique identifier and will be assigned to a specific attending anesthesiologist. The unique device identifier and corresponding attending anesthesiologist for each device will be recorded electronically with each quality use survey. A device use log will be established electronically from this data. If a device needs to be replaced, this will be noted in the electronic log and the new device unique ID number will be added to the electronic device record. Due to constraints entering the hospital at this time by research personnel, completeness of the electronic device logs will be assessed every other week for the duration of the study.

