7 STUDY INTERVENTION DISCONTINUATION AND PARTICIPANT DISCONTINUATION/WITHDRAWAL

7.1 Discontinuation of Study Intervention

Discontinuation from active participation using the study device does not mean discontinuation from the study, and remaining study questionnaires not yet completed at the time of discontinuation should be completed as indicated by the study protocol. Discontinuation of device use would occur if the subject user is unable to perform the airway procedure with the device in place. If a clinically significant finding is identified (including, but not limited to changes from baseline) after enrollment, the investigator or qualified designee will determine if any change in participant management is needed. Any new clinically relevant finding will be reported as an adverse event (AE) or ADE.

The data to be collected at the time of study intervention discontinuation will include the following:

- Completion of remaining study questionnaires, collection of patient clinical data and data regarding the intubation procedure from the medical record.

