7.2 Participant Discontinuation/Withdrawal from the Study

Participants are free to withdraw from participation in the study at any time upon request.

An investigator may discontinue or withdraw a user subject from the study for the following reasons:

- Significant biocontainment device use non-compliance
- If any clinical adverse event (AE) or ADE, or other medical condition or situation occurs such that continued participation in the study would not be in the best interest of the participant
- If the participant meets an exclusion criterion (either newly developed or not previously recognized) that precludes further study participation
- Participant unable to participate with device use for > 2 weeks.

An investigator may discontinue or withdraw a patient subject from the study for the following reasons:

- If any clinical adverse event (AE) or ADE, or other medical condition or situation occurs such that continued participation in the study would not be in the best interest of the participant
- If the participant meets an exclusion criterion (either newly developed or not previously recognized) that precludes further study participation

The reason for participant discontinuation or withdrawal from the study will be recorded on the Study Withdrawal Case Report Form (CRF). Patient subjects who sign the informed consent form and are randomized to use the biocontainment device but do not utilize the biocontainment device may be replaced. Patient subjects who sign the informed consent form and are randomized and use the biocontainment device, and subsequently withdraw, or are withdrawn or discontinued from the study, will be replaced.

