Airway procedure and patient data collection: Patient data and data from the anesthesia data record will be collected by PIs or their qualified designee post-airway procedure. As a result of social distancing and minimizing personnel due to COVID-19, it may not be possible to have a member of the research team present to observe and record data from each procedure. The airway procedures will be recorded using a GoPro camera placed in a fixed position. Data from the memory card will be transferred to an institutionally secured and managed network drive. Device use data will be collected from the videos by the PI or qualified designee. This data will include length of time to setup the device, length of time to perform the airway procedure, length of time to remove the device, number of times hand ports were used per procedure, and positioning of the torso drape. Patient data collected from the medical record will include patient demographics, contact information (phone and email), age, gender, race, co-morbid conditions (i.e. cardiac disease, lung disease, diabetes, BMI), smoking status. Airway procedure-related data that will also be collected will include BMI, hyomental distance, Mallampati score, type of airway procedure performed, number of attempts to perform the airway procedure, devices used for airway procedure, use of mask ventilation, anesthesia sequence used, and experience level of person performing the airway procedure.

Quality Use Survey and Safety Data Collection: As part of the study, user subjects will complete a Quality Use Survey after each day using the device. The results of the survey will be transferred from hard copies or REDCap to electronic format in CTMS for storage. This survey will collect user information on device functionality, perceived benefit of device use, healthcare burden associated with the device and safety data associated with device use. Safety data collected will include: 1) injury to the patient subject (patient in ABCD) or user subject (healthcare provider), 2) healthcare provider perceived patient subject anxiety or claustrophobia, 3) difficulty performing intubation with or without requiring removal of the device, 4) observed device defects or failures (i.e. broken strap, crack in plexiglass, break in hand ports).

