8.3.2 Classification of an Adverse Event

8.3.2.1 Severity of Event

Adverse events will be classified based on the defined grading system:

- Mild: events require minimal or no treatment and do not interfere with the participant's daily activities
- Moderate: events result in low level of inconvenience or cause some inference with functioning
- Severe: events interrupt a participant's usual daily activity. Severe events are usually potentially life-threatening or incapacitating. Please note, the term "severe" does not necessarily equate to "serious".

8.3.2.2 *Relationship to Study Intervention*

All adverse events (AEs) and ADEs must have their relationship to the study device assessed by the PI who examines and evaluates the participant based on temporal relationship and his/her clinical judgment. The degree of certainty about causality will be graded using the categories below. In a clinical trial, the study product must always be considered.

- Definitely Related – The AE/ADE is known to occur with the device.
- Probably Related – There is a reasonable possibility that the device caused the AE, or there is a temporal relationship between the device use and event. Reasonable possibility means that there is evidence to suggest a causal relationship between the device and the AE/ADE.
- Possibly Related - There is a possibility that the device caused the AE, or there is a temporal relationship between the device use and event. There is no evidence to suggest a causal relationship between the device and the AE/ADE but an alternate etiology has not yet been established.
- Unrelated – There is not a reasonable possibility that the use of the device caused the event, there is no temporal relationship between the use of the device and event onset, or an alternate etiology has been established.

8.3.2.3 *Expectedness*

Expected adverse events associated with this study that will be tracked and reported include:

1. Minor injury to the patient subject or provider
2. Patient claustrophobia
3. Patient anxiety
4. Difficulty performing intubation with the device in place
5. Need to remove the biocontainment device to safely perform intubation

Potential SAEs associated with this study would include:

1. Major physical injury to patient or provider due to device failure.

A UADE for this device would be breakdown or malfunction of the device during use.

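### The randomised airway-time comparison rests on an undefined per-protocol set, which can lose device-removal cases from the device arm only

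*Combined protocol and SAP*

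**What the plan says.** Section 6.3 sets the design: "Randomization will be done to assign patients to intubation with or without the biocontainment device in a 2:1 fashion". Section 4.1 offers this randomisation as the means of limiting bias. Section 9.3 then names one analysis population: "For this study, a per-protocol analysis dataset will be obtained". It is made up of user and patient subjects who complied, and no criterion for compliance follows.

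The sections where a criterion might be expected do not supply one:

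- Section 6.4, on intervention compliance, describes a source of information: "Use of the device will be assessed based on review of videos of the procedures", together with the surveys. It gives no threshold or rule.
- Section 7.1 stops device use when the user cannot complete the airway procedure with the device in place. It adds that "Discontinuation from active participation using the study device does not mean discontinuation from the study" and asks for procedure data to be collected. It does not say whether those data enter the 9.3 set.
- Section 7.2 has two replacement rules. Patients "randomized to use the biocontainment device but do not utilize the biocontainment device may be replaced", and those "randomized and use the biocontainment device, and subsequently withdraw, or are withdrawn or discontinued from the study, will be replaced". Both concern the device arm only, and neither says whether a replaced patient's airway time is kept.
- Section 8.3.2.3 lists among the expected events "Need to remove the biocontainment device to safely perform intubation".
- Section 9.4.2 says the primary analyses use all data points, and contrasts this with a sub-analysis of participants who have no missing data.

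**The concern.** Randomisation protects the comparison only if patients are compared in the groups to which they were assigned. Here the sole population is defined by what happened after assignment, and one foreseeable event, taking the device off because intubation is difficult, can occur in the device arm only. A removal case may be judged compliant or not. No control case faces that judgement.

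Airway time is a primary endpoint, and section 9.1 hypothesises that times are equivalent. The trial is unblinded. Section 8.1 says "Device use data will be collected from the videos by the PI or qualified designee", and the times come from the same videos. Section 9.1 has this endpoint analysed every two weeks, so with no prior definition compliance could be settled after times are known. If removal cases have long times and are left out, the comparison moves toward the hypothesis.

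Removals would not vanish from the report, because they are tracked as events and totalled under 9.4.2. What is at stake is the time comparison.

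**Working it through.** **The plan's own figure.** The only related number is the minimum of 97 procedures in section 9.2. From the second line of its calculation, 3.8416 × 0.25 / 0.01 = 96.04, rounded up to 97. That formula uses neither arms nor an analysis set, so the choice of population does not change it. The rest is a sensitivity range.

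**Inputs.** From the documents: 100 procedures with the device and 50 without (section 1.3), significance level 0.05 (9.4.1), ANOVA (9.4.2). Assumed, because the documents give none: SD 30 s; 2%, 5% or 10% of device cases with removal; 60 s or 180 s of excess time in those cases; two-sided testing.

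**Shift in the device-arm summary when removal cases are left out.** The mean falls by rate × excess. The median fall is the m that solves (1 − r)·Φ(m/30) + r·Φ((m − e)/30) = 0.5, where r is the rate and e the excess.

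| Removals | Excess | Fall in mean | Fall in median |
|---|---|---|---|
| 2% | 60 s | 0.02 × 60 = 1.2 s | 0.7 s |
| 5% | 60 s | 0.05 × 60 = 3 s | 1.9 s |
| 10% | 180 s | 0.10 × 180 = 18 s | 4.2 s |

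**Chance of p < 0.05, removal cases kept versus left out.** Simulation of 20,000 trials per case, with a fixed number of removals. ANOVA with two groups is the t test. The rank test (Mann-Whitney) stands for the non-parametric fallback in 9.4.1.

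| Other slowing in all device cases | Removals, excess | ANOVA | Rank test |
|---|---|---|---|
| none | 2%, 60 s | 0.05 vs 0.05 | 0.05 vs 0.05 |
| none | 5%, 60 s | 0.07 vs 0.05 | 0.07 vs 0.05 |
| none | 10%, 180 s | 0.47 vs 0.05 | 0.15 vs 0.05 |
| 10 s | 2%, 60 s | 0.55 vs 0.48 | 0.52 vs 0.46 |
| 10 s | 5%, 60 s | 0.65 vs 0.47 | 0.60 vs 0.45 |
| 10 s | 10%, 180 s | 0.97 vs 0.47 | 0.79 vs 0.45 |

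**Worst case, without a time scale.** Suppose the cases left out are exactly the slowest fraction r of a normal device arm. The mean then falls by φ(z)/(1 − r) SD, where z is the 1 − r quantile: 0.11, 0.20 and 0.27 SD for r = 5%, 10% and 15%. With a true delay of 0.3 SD, the chance of finding a significantly longer device time falls from 0.40 to 0.23, 0.11 and 0.06. With 0.5 SD it falls from 0.82 to 0.66, 0.49 and 0.32. If omission is unrelated to time, there is no bias.

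**The opposite effect.** Patients assigned to the device who never used it dilute a true slowing if kept in the device arm. With 10 s slowing and no removals, ANOVA rejection falls from 0.48 to 0.44 with 5 non-users and to 0.40 with 10. With 2 removals (60 s) and 10 non-users, the two effects cancel: 0.47 with everyone kept, 0.47 with both groups left out. With 5 removals (60 s) and 5 non-users, they do not: 0.62 against 0.47.

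**The case against.** The plan does not order the exclusion of removal cases, and it can be read the other way. Sections 2.3.1 and 2.3.3 describe quick removal as a path the protocol provides, so a user who takes it has arguably complied. Section 7.1 asks for the procedure data, and the end time in 9.4.2 is a secured airway, which does not depend on the device still being in place. The all-data-points sentence points to inclusion. This stands as a description of a sensible reading, and it is why the finding is that removal cases can be left out, not that they will be. But 9.3 does not say it. The 9.4.2 sentence is set against missing data: either it says nothing about the population, or it conflicts with 9.3.

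A per-protocol set has a recognised place under an equivalence hypothesis, and an as-randomised set containing non-users also drifts toward equivalence. This stands too. It is a reason to keep both sets and report non-use with reasons. It does not justify an undefined per-protocol set as the only one.

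The largest contrast, 0.47 against 0.05, comes from the extreme corner of assumed inputs, where the excess is six assumed SDs. Section 5.2 excludes known or anticipated difficult airways and section 2.3.3 calls inability to intubate a small risk, so the low end deserves equal weight. That is correct. Review of results by a neutral statistical third party (6.3) helps somewhat, but it does not define compliance.

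**Conclusion.** The concern holds. A randomised primary comparison has a per-protocol set as its only stated population, membership is undefined, and device removal and the replacement rules in 7.2 bear on the device arm alone. Confidence in this reading of the text is high.

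The size of any bias is not known. It requires that removals occur, that they take longer, and that they are judged non-compliant. Under the assumed inputs it runs from nothing that matters (2% and 60 s: mean 1.2 s, median 0.7 s) to a decisive change in the ANOVA (10% and 180 s: mean 18 s), while the median moves by no more than about 4 s. For removal cases that run long, the direction is toward the trial's hypothesis. For non-users and later withdrawals it cannot be stated in advance. This should be fixed: a primary endpoint is exposed and the correction is cheap.

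**What to change.** - **Section 9.3:** make the primary set for airway time all randomised patients whose airway procedure was started, analysed by assigned arm, with the interval from T0 to T1 kept if the device is removed. Keep the per-protocol set as a supportive analysis reported beside it. Define compliance before any analysis, including the two-weekly ones, and state whether a removal case meets the definition.
- **Section 7.2:** state that replaced patients stay in the analysis, as consent allows, and that replacements are additional.
- **Section 9.4.2:** reconcile the all-data-points sentence with 9.3 by saying whether it concerns missing values or the population.
- **Reporting:** give non-use and removals with reasons, by assigned arm, so that any dilution can be seen.

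The cost is wording. No new measurement is needed, because the schedule of activities already lists extraction from video and anesthesia records without restricting it to one arm. The rule is best settled before enrolment, since videos are deleted within 14 days of download to the server (10.1.8.1). The downsides are slightly less favourable device times, possibly wider intervals if a few times are very long, some dilution of a true slowing by non-users, and possibly a few additional patients.
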